	Email: [contact]
Inova Fairfax Hospital	[name]
lliova railiax nospitai	Inova Medical Group - Cardiology
FWA#: 00000573	[name]
	[name]
	[contact]
	E-mail: [contact]

^{*} No subject enrollment

Estimated Duration of Study:

[6 years]

Estimated Completion Date of Study:

December 31, 2023

Subjects of study and sites:

Subjects	Sex	Age range	Sites
60 screened	Men & Women	≥21 years	Up to 8
30 enrolled			

DISCLOSURES

The non-NIH investigators have the following conflicts of interest:

[name] serves as a proctor for Edwards Lifesciences and St Jude Medical.

[name] is a consultant for Edwards Lifesciences and for Abbott Vascular, and his employer has research contracts from Edwards Lifesciences, Abbott Vascular, Medtronic, St Jude Medical, and Boston Scientific.

[name] serves as a proctor for, and receives research support from, Edwards Lifesciences.

ABBREVIATIONS

СТ	Computed tomography
LAMPOON	Intentional laceration of the anterior mitral valve leaflet to prevent LVOT obstruction
	during TMVR
LVOT(O)	Left ventricular outflow tract (obstruction)
MVARC	Mitral valve academic research consortium (criteria)
MR	Mitral valve regurgitation
MS	Mitral valve stenosis
TAVR	Transcatheter aortic valve implantation
TEE	Transesophageal echocardiography
THV	Transcatheter heart valve
TMVR	Transcatheter mitral valve implantation

PRÉCIS

Transcatheter mitral valve replacement (TMVR) is an option to treat mitral valve failure when no surgical options exist. In as many as half of patients, TMVR can cause life-threatening blockage of the left ventricle by displacing the existing mitral valve leaflet. For these patient's the only options appear to avoid TMVR or in some to cause a focused heart attack and to wait 6 weeks. The investigators have developed and tested a technique to tear the existing mitral valve leaflet and enable TMVR in patients who have no other options. The procedure is called intentional laceration of the anterior mitral leaflet to prevent left ventricular outflow tract obstruction (LAMPOON). Although there are no dedicated TMVR devices commercially available, there has been short-term success with implanted transcatheter aortic valve devices in the mitral position for TMVR.

The purpose of this study is to perform LAMPOON and TMVR in patients who have no good options to treat their mitral valve failure, using heart valve devices designed to implant in the aortic valve position.

Table of Contents

1.0		Protocol Summary	8

1.0 Protocol Summary

Title:	NHLBI LAMPOON Study: Intentional laceration of the anterior mitral leaflet to prevent left ventricular outflow tract obstruction during transcatheter mitral valve implantation
Précis:	Transcatheter mitral valve replacement (TMVR) can cause life-threatening complications such as left ventricular outflow tract obstruction and transcatheter heart valve dysfunction, in cases of extreme septal displacement of the anterior mitral valve leaflet (AML).
	LAMPOON is a new catheter technique to split the AML and prevent iatrogenic left ventricular outflow tract obstruction immediately before TMVR. It mimics surgical chord-sparing AML resection. It has been used successfully in a small number of patients
Hypothesis:	LAMPOON enables transcatheter mitral valve implantation (TMVR) without life-threatening left ventricular outflow obstruction or transcatheter heart valve dysfunction
Objectives:	Technical success (defined below) of LAMPOON-TMVR Safety (Freedom from MACE to hospital discharge and 30days) of LAM- POON-TMVR
Safety Endpoints	Survival to discharge Survival to 30days Freedom from MACE (according to MVARC)
Feasibility Endpoints	Procedure technical success (TMVR with successful LAMPOON, without requiring bailout cardiac surgery or bailout septal reduction)
	Stratified analysis based on predicted LVOT obstruction or predicted THV dysfunction ("hanging leaflet")
Population:	Patients with native mitral valve failure (regurgitation or stenosis) after surgical mitral annuloplasty or from native mitral annular calcification, requiring transcatheter mitral valve replacement because of prohibitive risk of mitral valve surgery

Inclusion Criteria	Undergoing TMVR for valve-in-ring, valve-in-band, or valve-in MAC:
	Adults age ≥ 21 years
	Severe symptomatic native mitral valve failure after mitral annuloplasty repair or related to mitral annular calcification.
	Transcatheter mitral valve replacement (TMVR) is felt indicated by the multi- disciplinary institutional heart team, including at least one cardiovascular surgeon who has examined the patient
	High or prohibitive risk of LVOT obstruction (predicted neo-LVOT less than 200 mm ²⁾) or transcatheter heart valve dysfunction from long/redundant anterior mitral valve leaflet, as determined by the multidisciplinary institutional heart team.
	Anatomic eligibility for LAMPOON based on core lab assessment of the base-line CT and echocardiogram.
	Concordance of the study selection team
Exclusion Criteria	Subjects unable to consent to participate, unless the subject has a legally authorized representative
	Subjects unwilling to participate or unwilling to return for study follow-up activities.
	Predicted neo-LVOT created by the Sapien 3 skirt, after LAMPOON, less than 150 mm ²
	TAVR within 6 weeks
	Intended concurrent structural heart procedure, such as aortic or tricuspid valve implantation
	Pregnancy or intent to become pregnant prior to completion of all protocol follow-up procedures
Phase:	Phase IIa

Study Procedure	NHLBI Data Coordinating Center
	NHLBI + Local Institutional Review Boards
	Sites are trained by national PIs and NHLBI investigators
	Subjects are identified by site investigators
	CT and echo are analyzed by core laboratories
	Subject eligibility is confirmed by local multidisciplinary heart team including cardiac surgery, and is confirmed by study eligibility committee
	Subjects are enrolled prospectively
	Baseline and follow-up echocardiography are analyzed at Henry Ford Hospital core laboratory, and baseline and follow-up CT are analyzed at the NHLBI core laboratory; hemodynamics, fluoroscopy are analyzed at NHLBI
	Primary analysis based on 30-day outcomes; Secondary analysis includes 12-month outcomes
Sample Size	30 subjects at up to 8 sites
Risk-benefit determina- tion	These subjects have no therapeutic alternatives and have the potential to benefit from this procedure
Number of Sites enrolling participants:	8
Study Duration:	Six years
Participant Duration:	Five years

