3.0 BACKGROUND

The anterior mitral valve leaflet (AML) is a mobile structure that physically separates inflow and outflow zones of the left ventricle 1. Preserving the anterior mitral leaflet during surgical mitral valve replacement can cause LVOT obstruction, either when the prosthesis struts protrude into the LVOT or when a long redundant anterior leaflet prolapses into the LVOT 2, 3. In a similar manner, implantation of a transcatheter heart valve (THV) inside the native or repaired mitral valve enforces an "open position" of the anterior mitral valve leaflet that may encroach on the left ventricular outflow tract ⁴⁻⁷. This septal displacement of the AML is exaggerated when the aortic and mitral annular planes are acutely angulated rather than parallel, when the interventricular septum bulges towards the LVOT, when the AML is elongated, and when the implant extends or flares into the left ventricle. In this setting TMVR may cause life-threatening LVOT obstruction [Figure]. Moreover, after TMVR an excessively long AML may prolapse anteriorly into a narrowed LVOT as in hypertrophic cardiomyopathy, or it can prolapse posteriorly and interfere with bioprosthetic heart valve opening or closing by mechanical or Bernoulli effects after surgical ³ or transcatheter mitral replacement 8. Longer AMLs are more susceptible to these effects9. Although few data are available to guide decision-making, half of TMVR candidates having an intact AML in an ongoing clinical investigation [[name] personal communication, NCT02370511], are excluded because of the perceived risk of life-threatening LVOT obstruction.

One approach to prevent or treat TMVR-related LVOT obstruction is pre-emptive transcoronary alcohol septal ablation ^{10, 11}, which sacrifices myocardium, risks conduction system injury and pacemaker-dependence in patients with cardiomyopathy, which is unsuitable in patients with thin interventricular septa, and which delays TMVR by 4-6 weeks to allow remodeling in highly symptomatic patients. Another option is surgical anterior mitral leaflet resection combined with TMVR during thoracotomy and cardiopulmonary bypass ¹²⁻¹⁴, with attendant risk and comorbidity.

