7.0 ELIGIBILITY ASSESSMENT

7.1 Inclusion Criteria

- Adults age ≥ 21 years
- Severe symptomatic native mitral valve failure after mitral annuloplasty repair or related to mitral annular calcification.
- Unacceptably high or prohibitive risk for surgical mitral valve replacement and indicated for transcatheter mitral valve replacement (TMVR) as determined by the multidisciplinary institutional heart team, including at least one cardiovascular surgeon who has examined the patient
- High or prohibitive risk of LVOT obstruction (predicted neo-LVOT less than 200 mm²⁾ or transcatheter heart valve dysfunction from long/redundant anterior mitral valve leaflet, as determined by the multidisciplinary institutional heart team.
- Anatomic eligibility for LAMPOON based on core lab assessment of the baseline CT and echocardiogram.
- Concordance of the study selection team

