10.2 Study Analysis

Clinical events are classified by the local site Principal Investigator and confirmed by the Principal Investigator. The results of the study will be released within 12 months of study completion.

Analyses will be stratified according to the setting for TMVR, whether valve-in-ring, valve-in-band, or valve-in-MAC.

The study will be analyzed using descriptive statistics, including a case-by-case narrative summary of major adverse events. Afterwards, we will survey for parameters associated with an increased risk of major adverse events.

Primary and secondary endpoints will also be analyzed separately among patients with- and without- mitral annular calcification as the primary indication for TMVR.

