10.2.1 Primary endpoint

The primary endpoint is Technical success ACCEPTABLE (measured at exit from the catheterization laboratory)¹⁹. All of the following must be present:

- Successful LAMPOON traversal and laceration; and
- Peak LVOT gradient < 50 mm Hg; and
- Absence of procedural mortality; and
- Successful access, delivery, and retrieval of the LAMPOON device system; and
- Successful deployment and correct positioning of the first intended device; and
- Freedom from emergency surgery or reintervention related to the device or access procedure.

The first two factors are modifications of the MVARC (mitral valve academic research consortium) consensus endpoint¹⁹, specific for LAMPOON procedure.

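### Does the plan leave valve dysfunction from a long leaflet, the second half of its hypothesis, without an outcome or an analysis?

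*Combined protocol and SAP*

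**What the plan says.** The Protocol Summary (section 1.0) gives the hypothesis as "LAMPOON enables transcatheter mitral valve implantation (TMVR) without life-threatening left ventricular outflow obstruction or transcatheter heart valve dysfunction". Its précis pairs the same two harms, speaking of "life-threatening complications such as left ventricular outflow tract obstruction and transcatheter heart valve dysfunction". Section 7.1 admits a patient for high risk of LVOT obstruction, with a predicted neo-LVOT under 200 mm², "or transcatheter heart valve dysfunction from long/redundant anterior mitral valve leaflet, as determined by the multidisciplinary institutional heart team". Section 3.0 describes the leaflet mechanism: after implantation a long anterior leaflet may obstruct the outflow tract, or "it can prolapse posteriorly and interfere with bioprosthetic heart valve opening or closing".

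The two co-primary endpoints (10.2.1 and 10.2.2) are composites assessed on leaving the catheterization laboratory. Their only hemodynamic component is peak LVOT gradient, below 50 or below 30 mm Hg. The other components are successful traversal and laceration, no procedural death, successful handling of the LAMPOON system, correct placement of the first intended valve, and "Freedom from emergency surgery or reintervention related to the device or access procedure".

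Under feasibility endpoints the Protocol Summary lists "Stratified analysis based on predicted LVOT obstruction or predicted THV dysfunction". Section 10.2 says "Analyses will be stratified according to the setting for TMVR, whether valve-in-ring, valve-in-band, or valve-in-MAC", and adds a comparison with and without annular calcification as the indication for TMVR. It does not mention the split by predicted problem.

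**The concern.** A subject can enter because a hanging leaflet threatens the new valve, with no predicted outflow problem. That subject is then scored on an LVOT gradient that was never in doubt. A valve that is impaired but left untreated on leaving the laboratory would count as a success on both co-primaries. The exploratory list in 10.2.3 has device failure, paravalvular leak, device thrombosis and the MVARC composites, but nothing tied to the native leaflet. The adjudication list in 10.2.5 does not name it either.

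The split that would separate these subjects appears once, in the summary. It has no group definitions and no rule for a subject with both risks. If it were forgotten, leaflet-only subjects would be merged into the outflow result, and the second half of the hypothesis would be addressed only through general outcomes.

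**Working it through.** The plan derives no figure on this point, so the check is mainly a comparison of its sections.

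**1. Is the split planned?** Yes. Section 1.0 lists it. Section 10.2 names two other splits, by ring, band or MAC and by MAC or no MAC, and 10.2.3 adds subjects over 65. Nowhere does section 10 call its list complete or withdraw the one in the summary. The two places differ in coverage but do not conflict. Pooling without the split would mean departing from section 1.0.

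**2. Can the groups be formed?** Section 6.5 requires the heart team's eligibility determination and the inclusion criteria to be documented. Section 7.1 leaves the determination of both risks to the heart team. The natural grouping is the reason recorded at enrollment: outflow risk, leaflet risk, or both. This assumes the record distinguishes the two reasons.

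**3. What captures leaflet-related dysfunction?**

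| Where | Item | How it bears on the leaflet |
|---|---|---|
| 10.2.1, 10.2.2 | Successful traversal and laceration | Appendix A lists LAMPOON as the mitigation for redundant-leaflet dysfunction, so a failed laceration fails both co-primaries |
| 10.2.1, 10.2.2 | Correct positioning; no procedural death; no emergency surgery or device-related reintervention | Severe dysfunction recognized and acted on in the laboratory fails both |
| 10.2.3 | Device failure; MVARC device, procedure and patient success | General; the MVARC definitions are not in the documents, so their coverage can be neither credited nor ruled out |
| 1.0, 10.2 | Survival, MACE, case narratives of major adverse events | A serious leaflet event would be described individually |
| 6.4, 12.2.1 | Follow-up echocardiograms; CT said to be for surveillance of valve dysfunction | Images exist on which dysfunction can be seen |

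None of these is specific to the leaflet, but coverage goes beyond death, surgery and reintervention.

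**4. How large might the leaflet-only group be?** The documents give no count. Sections 2.0, 5.0 and 12.1.1 all describe the population as patients at risk of LVOT obstruction, which suggests that leaflet-only entrants are few. Section 10.2.4 states the main clinical aim as avoiding death from acute severe LVOT obstruction, so the gradient focus is deliberate.

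**5. What could a separate result show?** For zero events in n subjects, the exact (Clopper-Pearson) 95% upper limit is 1 − 0.025^(1/n). The values 3, 6 and 12 are assumptions; 30 is the planned sample in 10.1.

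- n = 3: 1 − 0.025^(1/3) = 70.8%
- n = 6: 1 − 0.025^(1/6) = 45.9%
- n = 12: 1 − 0.025^(1/12) = 26.5%
- n = 30: 1 − 0.025^(1/30) = 11.6%

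If all 6 of 6 were co-primary successes, the lower limit would be 0.025^(1/6) = 54.1%.

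**6. What depends on it?** Section 10.1 says the sample size was not statistically derived, and section 10.2 plans descriptive statistics. The stopping rules in 10.3 use 30-day mortality by ring/band and MAC stratum. None of them uses the indication for LAMPOON.

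**The case for a change.** The strongest case for a change is that the protocol itself treats the leaflet problem as a second target. It is in the hypothesis, it is a separate route into the study, and Appendix A gives it its own row. That row has severity 4, one level below life threatening, so a harmful but non-fatal dysfunction could pass the co-primaries. The remedy looks cheap, since echocardiograms before discharge and at 30 days are already scheduled and read by a core laboratory. Small numbers also favor showing the groups over pooling them.

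Part of this stands. No outcome is worded for the leaflet, the summary's split is not repeated in section 10.2, and an impaired, untreated valve can count as technical success. The co-primaries, though, claim only technical success at laboratory exit, and later valve function is left to the follow-up outcomes.

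The rest is weaker. The risk table is damaged in the text available: the neighboring LVOT obstruction row shows 5 and 1 with a score of 7. One digit from it is thin evidence against a précis that calls both harms life-threatening. The documents do not say that surface echocardiography can attribute dysfunction to the native leaflet. A leaflet-specific outcome added to a version dated August 2020, when enrollment was expected from April 2017, would be post hoc for every scan already read. Grouping by a mix of the later CT core-laboratory reading and heart-team judgment would replace the prediction that qualified the subject, and would create a group with neither risk.

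**Conclusion.** The textual observation is right, but no change is needed. The split by predicted problem is already promised, and an analyst can carry it out from the eligibility record. Leaving it out of section 10.2 is an editorial gap. The lack of a leaflet-specific outcome is a fair trade-off in a 30-subject feasibility study whose main aim is outflow protection. Such dysfunction is picked up indirectly through laceration success, valve positioning, reintervention, death, general device outcomes and follow-up imaging.

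The effect is on interpretation only, and its size cannot be computed because the leaflet-only share is not given. At the assumed sizes of 3 to 12, even a perfect record leaves an upper limit between 70.8% and 26.5%, so neither a new outcome nor a new grouping rule would settle the second half of the hypothesis. This conclusion assumes that the sponsor honors its own summary and that the eligibility record shows which risk applied.

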2.0 OBJECTIVE

[figure not shown]
The objective of this protocol is further to characterize the feasibility and safety of intentional laceration of the anterior mitral leaflet to prevent left ventricular outflow tract obstruction (LAMPOON), in patients who require transcatheter mitral valve replacement (TMVR) for native mitral valve failure, but who are at risk of left ventricular outflow tract (LVOT) obstruction.

In this protocol, we use a transcatheter heart valve (THV), marketed for implantation in the aortic or pulmonic positions, off-label. The THV device is the Sapien 3 marketed by Edwards Lifesciences.

It is important to discriminate the principal research objective, which is evaluation of the LAMPOON technique, from the off-label use of the significant risk medical device, the Edwards Sapien 3 THV, which is used in the clinical TMVR procedure.

3.0 BACKGROUND

The anterior mitral valve leaflet (AML) is a mobile structure that physically separates inflow and outflow zones of the left ventricle 1. Preserving the anterior mitral leaflet during surgical mitral valve replacement can cause LVOT obstruction, either when the prosthesis struts protrude into the LVOT or when a long redundant anterior leaflet prolapses into the LVOT 2, 3. In a similar manner, implantation of a transcatheter heart valve (THV) inside the native or repaired mitral valve enforces an "open position" of the anterior mitral valve leaflet that may encroach on the left ventricular outflow tract ⁴⁻⁷. This septal displacement of the AML is exaggerated when the aortic and mitral annular planes are acutely angulated rather than parallel, when the interventricular septum bulges towards the LVOT, when the AML is elongated, and when the implant extends or flares into the left ventricle. In this setting TMVR may cause life-threatening LVOT obstruction [Figure]. Moreover, after TMVR an excessively long AML may prolapse anteriorly into a narrowed LVOT as in hypertrophic cardiomyopathy, or it can prolapse posteriorly and interfere with bioprosthetic heart valve opening or closing by mechanical or Bernoulli effects after surgical ³ or transcatheter mitral replacement 8. Longer AMLs are more susceptible to these effects9. Although few data are available to guide decision-making, half of TMVR candidates having an intact AML in an ongoing clinical investigation [[name] personal communication, NCT02370511], are excluded because of the perceived risk of life-threatening LVOT obstruction.

One approach to prevent or treat TMVR-related LVOT obstruction is pre-emptive transcoronary alcohol septal ablation ^{10, 11}, which sacrifices myocardium, risks conduction system injury and pacemaker-dependence in patients with cardiomyopathy, which is unsuitable in patients with thin interventricular septa, and which delays TMVR by 4-6 weeks to allow remodeling in highly symptomatic patients. Another option is surgical anterior mitral leaflet resection combined with TMVR during thoracotomy and cardiopulmonary bypass ¹²⁻¹⁴, with attendant risk and comorbidity.

4.0 CLINICAL AND SCIENTIFIC JUSTIFICATION

As an alternative, we have developed a simple transcatheter adjunct to TMVR, and described its preclinical use ¹⁵. This technique resembles Tirone David's surgical anterior resection with chordal sparing ¹⁶ which has become widely adopted as a method of surgical mitral valve replacement. We create a longitudinal split of the middle scallop (A2) of the AML, immediately before TMVR. As a result, chordal attachments displace the split AML away from the LVOT after the cylindrical THV is implanted, and blood flows unobstructed across the THV stent struts [Figure 1].

We recently reported the initial human experience with this intentional Laceration of the Anterior Mitral leaflet to Prevent left ventricular Outflow tract Obstruction (LAMPOON) procedure ¹⁷. Five patients with prohibitive risk of LVOT obstruction or transcatheter heart valve (THV) dysfunction from TMVR successfully underwent LAMPOON, with longitudinal splitting of the A2 scallop of the AML, prior to valve implantation. Multiplane CT modelling predicted hemodynamic collapse assuming an intact AML. However, critical LVOT gradients were not seen following LAMPOON and TMVR. Doppler blood flow was seen across THV struts that encroached the LVOT, because the AML was split. Transcatheter heart valve function was unimpeded. We concluded that this novel catheter technique, which resembles surgical chord-sparing AML resection, may enable TMVR in patients with prohibitive risk of LVOT obstruction or THV dysfunction.

Recently there have been reports of late transcatheter heart valve thrombotic dysfunction¹⁸. This warrants further investigation using follow-up imaging.

[figure not shown]
